8.1 Ethics approval

Prova Health will obtain approval from a provider of Institutional Review Board (IRB) services based in the US. The study will be conducted in accordance with the recommendations for physicians involved in research on human subjects adopted by the 18th World Medical Assembly, Helsinki 1964 and later revisions.

8.2 Consent

Consent to enter the study must be sought from each participant only after a full explanation has been given, with an information leaflet offered and time allowed for consideration. Signed participant consent should be obtained. The right of the participant to refuse to participate without giving reasons must be respected. All participants are free to withdraw at any time.

8.3 Confidentiality

The Study Management Team will preserve the confidentiality of participants taking part in the study and fulfil transparency requirements under the General Data Protection Regulation for health and care research. Data and all appropriate documentation will be stored for a minimum of 10 years after the completion of the study.

8.4 Indemnity

Prova Health and its subcontractors hold negligent harm insurance policies which apply to this study.

8.5 Sponsor

Prova Health will act as the main Sponsor for this study.

8.6 Funding

Hoffman-La Roche Ltd. are funding this study under the terms of the Research Agreement for an Investigator Initiated Study entered into between Prova Health and F. Hoffmann-La Roche Ltd.

Participants will be compensated for their time, with the amount varying by level of experience, as specified by Roche HCP Services Fair Market Value Guidelines. For those deemed Local Thought Leaders, compensation will be no more than \$400 per hour; those deemed Region Thought Leaders will be compensated at a rate of no more than \$520 per hour; those deemed National Thought Leaders will be compensated no more than \$660 per hour.

10. PUBLICATION POLICY

The results of the study will be written up in a report for Roche Information Solutions. Pseudonymised quotes from participants may be published along-side their job role. Participants will not be named in any reports/publications.

11. APPENDICES

Appendix A: Post-Simulation Survey (attached separately)

Appendix B: Interview guide

Intro

What are semi-structured interviews?

Semistructured in-depth interviews are commonly used in qualitative research and are the most frequent qualitative data source in health services research. This method typically consists of a dialogue between researcher and participant, guided by a flexible interview protocol and supplemented by follow-up questions, probes and comments. The method allows the researcher to collect open-ended data, to explore participant thoughts, feelings and beliefs about a particular topic and to delve deeply into personal and sometimes sensitive issues.

Source: Semi-structured interviewing in primary care research: a balance of relationship and rigour

Objectives of semi-structured interviews:

- **Understand current practice for oncology workflows** in a patient's cancer care journey by:
 - Identifying and defining common denominators in the oncology workflow (characterize from each interviewee's experience: 1. actors involved, 2. workflows and interactions)
 - Understanding what kind of data matters, depending on the current phase of a patient's oncology care journey - across diagnostic workup, treatment planning and treatment management (which milestones matter? Diagnostic information, treatment response, relapses, treatment-related issues, etc.)
 - Understanding how healthcare IT systems are used in the oncology workflow to access data and coordinate care (cost and resource effectiveness, cognitive burden, user satisfaction, level of doctor-patient engagement, etc.)
- Inform the design of a study protocol and validate use cases for NAVIFY® Oncology Hub using clinical simulation.
 - Collect information on actual and/or potential use of NAVIFY®
 Oncology Hub in the interviewee's practice with the objective to build the case for integrating NAVIFY® Oncology Hub into the workflow.
 - **Identify the most appropriate outcome measures** for the utility of NAVIFY® Oncology Hub in clinical practice.

NAVIFY Oncology Hub - Interview script

Introduction

Thank you for participating in this interview. We are seeking to understand how oncologists access cancer patient data and coordinate care in clinical practice. This project is funded by Roche/Genentech and the insights will be used to inform the design of a research study to evaluate a clinical workflow and decision support solution.

The interview will be recorded and will be used by Prova Health for note-taking only - it will not be shared with Roche/Genentech or with anybody else outside of the Prova Health team.

Do you have any questions before we start? *Answer any questions*.

Before we begin, are you happy for me to start the recording? *Start the recording*.

Interview Section	Questions
(i) Demographics	What is your role at the cancer center?
	Probes:
	 How long have you worked here? What is the practice size and type? (eg. office based, clinical in-patient unit, academic center etc.) How many cancer patients per week would you typically see? Can you describe your clinical experience in oncology? How many years have you been working in this field? Do you work primarily for the cancer center or do you practice at multiple organizations?
(ii) Current clinical practice	We will ask you a number of questions on how you currently manage cancer patients in your practice. It will be important for us to understand as much as possible about how you conduct your consultations with cancer patients.
	What information/data do you look at prior to consulting with a cancer patient ?
	Probe:
	Why is this data important?How long does it take you to gather this data?

	Can you talk us through, step-by-step , how you would come up with a management plan for a cancer patient during a consultation?
	Probe:
	 What factors make the consultation productive or challenging?
(iii) Usage of healthcare IT systems	We will ask you a number of questions on how you use healthcare IT systems to access patient data and coordinate care.
	Can you describe how healthcare IT systems support your current workflow?
	Probe:
	 What healthcare IT system(s) do you use? How easy is this system to use? How productive are you able to be with this system? Can you walk us through how your healthcare IT systems facilitate complex treatment decisions?
(iii) Barriers with current healthcare IT systems	What factors make the consultation challenging with the current healthcare IT systems? Probe:
	 Thinking about the entire visit continuum, from pre-visit prep to the consultation, what kind of barriers to care exist with current healthcare IT systems? (e.g. effectiveness, cost, cognitive burden, patient engagement, provider satisfaction) How do you assess whether a healthcare IT system in your workflow was a worthwhile investment of your time and resources?
(iv) Use cases for NAVIFY® Oncology Hub	Thank you. We will now ask some questions about potential use cases for NAVIFY® Oncology Hub.

New patient consultation	Can you talk us through, step-by-step , how you use healthcare IT systems when assessing a new cancer patient?
	Probe:
	 What parts of the consultation do they help with? Can you access all data from one system, or do you have to deal with multiple systems?
Returning patient, follow-up visit	Can you talk us through, step-by-step , how you use healthcare IT systems when assessing returning cancer patients ?
	Probe:
	 What parts of the consultation do they help with? Can you access the most relevant data for follow-up patients quickly?
	 What additional information would have been helpful for you to have had on your returning patients?
Cross team care coordination	Can you describe how healthcare IT systems support your workflow in conveying information and coordinating care with other providers in the care team?
	Probe:
	 Can you talk us through, step-by-step, how you would coordinate care with other providers? Are you able to quickly and concisely convey information and coordinate care between providers? Overall, do you think healthcare IT systems improve cross team care coordination? If yes, how do they help? Do you believe they have any impact on outcomes? What metrics would you use to help assess a good 'outcome' for cross team care coordination?
Facilitating patient discussions and education	How do you use healthcare IT systems to facilitate discussion or to educate your patients (if at all)?
	Probe:
	 Have healthcare IT systems improved your patient interactions? Has it hurt your interactions with patients in any way? How much time do you spend communicating with patients?

Enrichment of patient record	How do you access and synthesize unstructured data on patient records? For example, a PDF report of a patient's biopsy results.
------------------------------	---

Conclusion

This brings us to the end of our interview. Thank you very much again for taking the time out to speak with us. As a next step, we will share a payment form for you to complete so that we can process payment for this interview. Before we finish, do you have any further questions?

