2.1 Study objectives

This work is designed as a 2-phase study.

Phase 1 objectives (semi-structured interviews):

- 1. Understand current clinical practice
- 2. Validate use cases of NAVIFY Oncology Hub

Phase 2 objectives (simulation study):

- 1. To assess the usability of NAVIFY Oncology Hub
- 2. To assess the efficiency of using NAVIFY Oncology Hub
- 3. To assess the mental effort required with using NAVIFY Oncology Hub
- 4. To gather feedback on the study methods

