3. STUDY DESIGN

This study will run over 2 phases.

Phase 1 (semi-structured interviews) – We will conduct a total of 12 semi-structured interviews with 12 US oncologists. These interviews will seek to:

(i) Understand incumbent clinical practice for activities that NAVIFY Oncology Hub is seeking to improve, for example, accessing cancer patient data, and care coordination.
(ii) Validate use cases of NAVIFY Oncology Hub and its perceived benefits, for example, reducing cognitive burden, increasing shared decision-making, etc.

There are 5 proposed use cases for NAVIFY Oncology Hub:

- 1) New patient consultation
- 2) Returning patient, follow-up visit
- 3) Cross team care coordination
- 4) Facilitating patient discussions and education
- 5) Enrichment of the patient record

The results from Phase 1 will inform potential adjustments to simulation study procedures for Phase 2, such as the duration of the simulation sessions.

An interview guide has been provided in Appendix B.

Phase 2 (simulation study) – This phase of the study will have approximately 30 US oncologists. We will first conduct a small number of simulation sessions (3-5) to validate study methods and data collection procedures. Study methods may then be refined before conducting simulation sessions with a larger number of participants (approx. 25).

In this phase, each participant will participate in a 90-minute simulation session in which they will use NAVIFY Oncology Hub to review synthetic patient cases. Participants will be tasked with reviewing the cases as if they were preparing to see a patient in a real clinical setting. This task will involve searching for, identifying, reviewing and synthesizing relevant clinical information (demographic information, pathology reports,

> Protocol No: HLR-NOH-001 Version No: v2.0 Date: 6 May 2022

clinical course, etc.) that supports decision-making. As such, this task is meant to simulate the same activities they would perform in their typical practice before inviting a patient into the clinic room for a consultation, and will permit this study to examine the usage of NAVIFY Oncology Hub on those activities.

Ultimately, the aim of the study is to investigate how NAVIFY Oncology Hub improves efficiency and reduces cognitive burden associated with reviewing and synthesizing patient information, and having participants engage with the platform requires them to go through those tasks.

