5.2 Conduct of semi-structured interviews

Semi-structured interviews: Participants will participate in a 60-minute remote (e.g., online) interview. A topic guide for the interview can be viewed at Appendix B. During scheduling, participants will be given a link to use to join the session. This link will take them to a video conference call hosted through Google Meet. The interviewer will use Google Meet to record the participant's audio. At the conclusion of the session, participants will be compensated.

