5.3 Conduct of simulation sessions

Simulation sessions: Participants will participate in a 90-minute remote (e.g., online) simulation session. During scheduling, participants will be given a link to use to join the session. This link will take them to a video conference call hosted through Google Meet. At the session, the moderator will facilitate the session and take notes. The moderator will be a member of the Prova Health team with clinical practice

experience. At the beginning of the session, participants will be instructed to share their screen with the moderator so that participants' use of NAVIFY Oncology Hub can be recorded. The moderator will then use Google Meet to record the participant's screen. Participants will be instructed to turn off their camera to preserve anonymity while ensuring data retention. At the conclusion of the session, participants will be compensated.

Activity	Duration (mins)
Introductions and consent	5
Review of simulation session guide	5
Training on NAVIFY Oncology Hub	20
Prepare 10 cases using NAVIFY Oncology Hub	50
Post-Simulation Survey	10
Total	90

A timeline of the simulation sessions is provided below.

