7. ANALYSIS

Thematic analysis of interview outputs will be performed by reviewing recordings from study participants in Phase 1. This analysis seeks to validate potential benefits and use cases for NAVIFY Oncology Hub, especially in areas such as accessing cancer patient data, care coordination, cognitive burden and shared decision-making.

Data from the simulation sessions will involve calculating summary descriptives (e.g., means and percentages) on case-specific endpoint measures. Counts or percentages may also be calculated on tabulated responses to survey questions to determine whether certain themes regarding the study participants' participation experience prove common across the participants and, therefore, warrant attention.

8. **REGULATORY ISSUES**

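### Phase 1 is meant to validate NAVIFY's use cases and perceived benefits, but none of the 19 scripted use-case questions asks about NAVIFY, and neither the script nor section 5.2 describes it

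*Combined protocol and SAP*

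**What the plan says.** Three sections of the protocol give the Phase 1 interviews a task specific to the product:

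- Section 2.1, Phase 1 objective 2: "Validate use cases of NAVIFY Oncology Hub".
- Section 3, aim (ii): "Validate use cases of NAVIFY Oncology Hub and its perceived benefits". The examples given are lower cognitive burden and more shared decision-making. The five use cases listed are new patients, returning patients, cross-team coordination, patient discussion and education, and enrichment of the record.
- Section 7, on the thematic analysis of the interviews: "This analysis seeks to validate potential benefits and use cases for NAVIFY Oncology Hub".

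Appendix B adds an objective of its own: "Collect information on actual and/or potential use of" the product in the interviewee's practice. Section 5.2 refers to the appendix for content ("A topic guide for the interview can be viewed at Appendix B") and otherwise covers length, the video link, recording and payment.

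In part (iv) of the script, on use cases, NAVIFY appears in the heading and in one transition sentence. The questions that follow are about healthcare IT systems in general or about the interviewee's present practice, for example "how you use healthcare IT systems when assessing a new cancer patient". The spoken introduction says that the results will be used "to inform the design of a research study to evaluate a clinical workflow and decision support solution". It neither names the product nor says what it does.

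**The concern.** Asking oncologists how they work now, and where their present systems fall short, can show a need or the lack of one. It does not show that they would use a particular product for that need, or that they expect it to help. Under the plan, the first kind of material would be analysed and reported as the second.

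The difference matters because section 2 says the evidence is to serve product development and market launch. A finding that a need exists and a finding that NAVIFY is seen to meet it support different claims. If the script is followed exactly, only the first is systematically available from Phase 1.

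**Working it through.** No sample size, power or error-rate calculation bears on this point. The check is a count of the scripted questions and a comparison of the objectives with what is asked.

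**Count of question sentences in Appendix B**, leaving out the opening and closing invitations to ask questions:

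| Part of script | Lead | Probe | Total | Ask about NAVIFY |
|---|---|---|---|---|
| (iv) New patient | 1 | 2 | 3 | 0 |
| (iv) Returning patient | 1 | 3 | 4 | 0 |
| (iv) Cross-team coordination | 1 | 6 | 7 | 0 |
| (iv) Patient discussion and education | 1 | 3 | 4 | 0 |
| (iv) Enrichment of record | 1 | 0 | 1 | 0 |
| **Part (iv)** | **5** | **14** | **19** | **0** |

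The earlier parts have 7 (demographics) + 5 (current practice) + 5 (use of IT systems) + 3 (barriers) = 20 questions, none about NAVIFY. The whole script has 20 + 19 = 39. If the short follow-up in the coordination block is merged with the question before it, part (iv) has 18; the number about NAVIFY is still 0.

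**Objectives against questions:**

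- *Expected use of NAVIFY in each use case:* no question.
- *Expected benefit or drawback of NAVIFY:* no question. Of the two example benefits in aim (ii), cognitive burden appears only as an example in a probe about barriers with current systems. Shared decision-making is named in no question, although the patient-education block comes near it.
- *Actual use of NAVIFY:* no direct question. A current user might mention it when asked which systems they use.

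**What interviewees can be assumed to know.** The eligibility criteria in section 4 do not require experience with NAVIFY. No sentence in the script or in section 5.2 says what it does. By contrast, the Phase 2 timeline in section 5.3 (conduct of simulation sessions) gives 20 of its 90 minutes to "Training on NAVIFY Oncology Hub".

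**Whether Phase 2 fills the gap.** Section 3 describes the Phase 2 task as reviewing synthetic cases before the patient is called in. That task clearly does not exercise two of the five use cases: cross-team coordination, and patient discussion and education.

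**Interview time for added questions.** If all 39 questions were asked in 60 minutes, the pace would be 60 / 39 = 1.54 minutes each. Two questions for each of five use cases is 10 questions, and 10 × 1.54 = 15.4 minutes, or 15.4 / 60 = 26% of the interview.

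**The case against.** The best defence is that exploring need is a fair way to validate a use case. The blocks in part (iv) follow the five named use cases, come after a spoken line that names NAVIFY, and probe functions the platform claims to offer, such as having data in one place and reaching it quickly. This has force for the words *use cases*. It does not cover the perceived benefits in aim (ii) or the potential use in the guide's own objective, both of which require asking about the product.

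Other points on that side:

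- *The guide is flexible, so interviewers can ask about NAVIFY unscripted.* True. But improvised questions may differ across 12 interviews, and an objective stated in three sections should not depend on them.
- *The leaflet offered before consent (section 8.2) may describe NAVIFY.* It may, and nothing can be concluded from its absence here. Even so, no scripted question would collect a reaction to it.
- *The Phase 2 survey collects product feedback after hands-on use* (sections 6.1 and 6.2), *and one line in Appendix B links use-case validation to simulation.* This is a real source of evidence about NAVIFY. But sections 2.1, 3 and 7 place this validation in Phase 1, and Phase 2 participants will not have tried coordination or patient education. The full survey is attached separately and cannot be judged here.
- *The only stated use of Phase 1 results within the study is to adjust Phase 2 procedures.* This limits the harm inside the study. It does not limit what section 7 would let the report say.
- *Opinions on a product that has not been demonstrated are hypothetical.* This stands. Added questions would yield perceived fit and expected benefit, and should be reported as such.

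**Conclusion.** The concern holds. As scripted, 0 of 19 use-case questions and 0 of 39 questions overall ask about NAVIFY, and neither the script nor section 5.2 describes it. Phase 1 can meet its first objective, understanding current practice, and can show need or lack of need in each use-case area. It cannot systematically support the second objective so far as that concerns the perceived benefit and potential use of NAVIFY itself. For two of the five use cases, the Phase 2 task clearly gives no hands-on experience to make up for this.

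The conclusion rests on the scripted text alone. It assumes nothing about what interviewers might improvise or what the leaflet contains. One of the two Phase 1 objectives is affected, and the mismatch should be resolved before the interviews begin.

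**What to change.** Either of two changes would bring the objective and the script into line.

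1. **Ask about NAVIFY.** Open part (iv) with a short standard description of the product, the same for every interviewee. Under each use case add the same two open questions: whether the interviewee would use NAVIFY for this, and why or why not; and what would get better or worse than with their current system. State in section 7 that the thematic analysis will code reasons against use as well as benefits. This needs an amended guide and about 15 minutes for the 10 questions at an even pace, plus the time for the description. Dropping some general IT probes would offset this. No extra participants are needed.

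2. **Narrow the claim.** Reword Phase 1 objective 2 (section 2.1), aim (ii) (section 3) and the first paragraph of section 7 as an assessment of current practice and unmet need in the five areas, and remove the word *validate*. The corresponding objectives in Appendix B should be brought into line. This takes no interview time.
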